#### 10.3.1 Primary Endpoint Analysis

The primary endpoints for the study are safety and feasibility.

Safety endpoint will be summarized by treatment group using quantitative and descriptive statistics of adverse events. Adverse events will be assessed according to the NIH Common Terminology Criteria for Adverse Events (CTCAE) v4.0 for scale grading adverse events. Related adverse events will be analyzed separately for those related to ADRCs and to the delivery of ADRCs (i.e. intravenous delivery), and for those related to tissue harvest.

Feasibility will address the following:

- Ability to perform tissue harvest and obtain 100-150 mL of adipose tissue
- Completion of dose preparation with the target dose
- Ability to deliver ADRCs via intravenous administration
- Successful secondary endpoint evaluations

#### ***10.3.2 Key Secondary and Exploratory Endpoint Analysis***

The key secondary endpoints are

- Percent epithelialization
- Graft take
- Proportion of population with complete wound closer

Epithelialization will be assessed by surgeon visual evaluation and blinded independent review of standardized digital photographs. Graft take will be assessed as the area over which vascularization is evident, and sufficient anchorage to the underlying tissue exists to support epidermal growth. Take will be expressed as a percentage of the area originally covered by the graft. Percent take is estimated separately for each of the grafted study sites. The proportion of subjects with complete wound healing will be determined and is defined as skin re-epithelialization without drainage or dressing requirements.

All other secondary endpoints will be treated as exploratory. P-values for each analysis will be computed separately, without any corrections for multiple comparisons. These analyses will be considered as part of the totality of the evidence concerning the safety and effectiveness of the product.

#### **10.4 Background, Demographic and Concomitant Medication Analyses**

Demographic data, medical history, concomitant disease and concomitant medication will be summarized by means of descriptive statistics (n, mean, SD, median, minimum and maximum) or frequency tables.

#### **10.5 Withdrawal, ITT, PTE**

Reasons for withdrawal pre- and post-randomization will be summarized. The treatment analyses will be performed on intent-to-treat basis as well as on a per-treatment-evaluable basis, as defined below:

Intent-to-Treat (ITT): All randomized subjects; randomization will occur on procedure day prior to the tissue harvest procedure. Subjects will be included in the analysis according to the treatment assigned if population is different than PTE.

Per-Treatment-Evaluable (PTE): All enrolled subjects who have day 5 follow-up information available.

#### **10.6 Handling of Missing Data**

Given the relatively small sample, missing data will not be imputed.

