##### ***4.6.2 Key Secondary Endpoints***

- Percent epithelialization of the graft at time of first dressing change and day 10 (only if wound dressing change planned) and weeks 2, 3 and 4
- Percent take of the graft at time of first dressing change and day 10 (only if wound dressing change planned) and weeks 2, 3 and 4

Digital photography will be performed at surgery and at each follow-up visit for blinded independent review.

Graft take will be assessed as the area over which vascularization is evident and sufficient anchorage to the underlying tissue exists to support epidermal growth. Take will be expressed as a percentage of the area originally covered by the graft. Percent take should be estimated separately for each graft-treated site.

Both of the above endpoints will be evaluated by (a) visual inspection by the treating surgeon, and (b) standardized digital photography and scoring centrally by a blinded trained assessor.

- Percent of group with complete wound closure at each assessment through to 12 weeks

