### 8.3 Burn Evaluations

The physical characteristics of the selected burn areas and the graft (up to 3 per subject) as well as the subjective evaluation of symptoms will be evaluated using several assessment tools. The assessment tools are listed below and detailed information and instructions provided in the *Study Reference Manual*. Planned study days are listed below but an acceptable range of days (±) is in the schedule of events.

- Percent epithelialization at early dressing changes (estimated time of first dressing change and day 10 after graft application and at weeks 2, 3 and 4 (by surgeon evaluation and blinded independent review of standardized photographs)
- Percent take of the graft at early dressing changes (estimated time of first dressing change and day 10 after graft application (if wound dressing must be changed) and at weeks 2, 3 and 4
- Occurrence of complete wound healing at each assessment weeks 4 to 12
- Transepithelial water loss at weeks 2, 3 and 4
- Wound pain VAS at time of first dressing change and day 10 and weeks 2, 3 and 4
- Pruritis VAS at 3, 4, 8, 12, 26 and 52 weeks
- Patient and Observer Scar Assessment Scale (POSAS) at 3, 4, 8, 12, 26 and 52 weeks
- Vancouver Scar Scale at 12, 26, and 52 weeks
- Skin elasticity measurement at 12, 26 and 52 weeks (Delfin SkinElastimeter)
- Skin pigmentation (Delfin SkinColorCatch) measurement at weeks 12, 26, and 52
- Skin hardness (Delfin SkinFibrometer) measurement at weeks 12, 26, and 52

- Percent of wounds with complete wound closure at weeks 2, 4, 8 and 12
- Digital photography of treated wounds on day 1 and each follow up visit
- Biomarkers related to burn injury will be assessed from 4-5mL blood (serum) samples drawn at baseline (prior to treatment), time of first dressing change and day 10 and weeks 2, 3, 4, 8 and 12 post-ADRC administration.

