## 10 STATISTICAL METHODS AND DATA ANALYSIS

The RELIEF Trial is a multi-center, open-label, randomized, usual care controlled study to evaluate the feasibility and safety of ADRCs with usual care compared to usual care alone in subjects with thermal burns. The primary endpoint will be safety and feasibility.

The ITT population will be used for the primary analysis; the analysis will also be presented in the PTE population.

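### A blanket no-imputation rule and an unstated denominator let subjects who die or leave with an open wound drop out of the ITT closure percentages

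*Protocol*

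**What the plan says.** The missing-data section (Protocol 10.6) reads "Given the relatively small sample, missing data will not be imputed". It does not distinguish between types of endpoint or reasons for missing data.

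Section 10.5 defines "Intent-to-Treat (ITT): All randomized subjects" and applies ITT, alongside the per-treatment-evaluable set, to the treatment analyses. The opening of section 10 adds: "The ITT population will be used for the primary analysis; the analysis will also be presented in the PTE population".

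Complete closure is a key secondary endpoint. Section 4.6.2 words it as "Percent of group with complete wound closure at each assessment through to 12 weeks". Section 10.3.2 says "The proportion of subjects with complete wound healing will be determined and is defined as skin re-epithelialization without drainage or dressing requirements". Section 8.3 also lists "Percent of wounds with complete wound closure at weeks 2, 4, 8 and 12", which changes the unit from subject to wound. Section 10.3 summarizes categorical data as counts and percentages without naming a denominator. No section says how a subject who dies or withdraws before an assessment is counted.

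Appendix A schedules closure at weeks 2, 3, 4, 8 and 12 only. Section 5.5 gives the early-termination visit the content of the next scheduled visit. Section 8.11 gives it the content of Week 52, where closure is not scheduled.

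**The concern.** A subject who dies, or leaves the study, with the wound still open has not achieved closure while under study. That is information about the endpoint and not just a blank cell. If the blank removes the subject from both numerator and denominator, the percentage describes only those who stayed, and the arm that lost a larger share with open wounds gains in apparent healing.

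Such losses are foreseeable. Subjects have burns of 20% to 50% TBSA. Entry excludes only those not expected to survive beyond 30 days, while closure is followed to week 12. Treatment is open-label, so withdrawal may differ by arm. One route exists only in the ADRC arm: section 10.3 makes full follow-up optional for harvested subjects whose cells fail release, yet keeps them in ITT for efficacy.

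Section 10.2 says the data are meant to support the design of a larger study. Distorted closure estimates would carry over into that design.

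**Working it through.** The protocol gives no closure rate, loss rate, effect size or power, so there is no figure of its own to reproduce. The closure rates and loss counts below are assumptions.

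**Inputs from the protocol.** Up to 15 subjects (section 4.3) randomized 2:1 (section 5.2): 15 × 2/3 = 10 ADRC and 15 × 1/3 = 5 usual care. The unit is the subject, as in section 10.3.2.

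**Formulas.** Let n be the number randomized to an arm, h the number closed at a visit, and m the number lost earlier with an open wound.

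- Observed-case percentage: h/(n − m)
- All-randomized percentage, counting the m as not closed: h/n
- Ratio of the two: n/(n − m) = 1/(1 − m/n), so the inflation depends on the share lost, m/n.

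**Equal true closure of 60% (6/10 and 3/5).**

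| Lost open, ADRC / control | Observed ADRC | Observed control | Difference (points) |
|---|---|---|---|
| 0 / 0 | 6/10 = 60% | 3/5 = 60% | 0 |
| 1 / 0 | 6/9 = 66.7% | 60% | +6.7 |
| 2 / 0 | 6/8 = 75% | 60% | +15 |
| 3 / 0 | 6/7 = 85.7% | 60% | +25.7 |
| 0 / 1 | 60% | 3/4 = 75% | −15 |
| 0 / 2 | 60% | 3/3 = 100% | −40 |
| 1 / 1 | 66.7% | 75% | −8.3 |
| 2 / 1 | 75% | 75% | 0 |

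With all randomized subjects as denominator, every row gives 60% versus 60%, a difference of 0.

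**Other assumed closure rates.**

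- At 80% (8/10 and 4/5): one ADRC loss gives 8/9 = 88.9% (+8.9), two give 8/8 = 100% (+20), and one control loss gives 4/4 = 100% (−20).
- At 40% (4/10 and 2/5): one ADRC loss gives 4/9 = 44.4% (+4.4), two give 4/8 = 50% (+10), one control loss gives 2/4 = 50% (−10), and two give 2/3 = 66.7% (−26.7).

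**The order can reverse.** With 5/10 closed under ADRC and three lost open, the observed figure is 5/7 = 71.4%, against 3/5 = 60% for usual care with none lost. The true order is 50% versus 60%.

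**Losses after healing act the other way.** If one or two of the six closed ADRC subjects are lost, the observed figures are 5/9 = 55.6% and 4/8 = 50%, against 60%.

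**Testing.** The Fisher exact test was applied to the observed-case tables with equal true closure. The smallest p-value is 0.385 (8/8 versus 4/5). The distortion lies in the estimates.

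**The case against.** The strongest objection is that removal from the denominator is inferred. Section 10.6 bars imputation; it does not say that subjects without a value are dropped. A percentage of the group, read with ITT as all randomized, could mean documented closures divided by everyone randomized, which would count the lost as not closed. This stands as a limit: a reader might conclude that the protocol fixes a complete-case analysis, and the text does not go that far. But counting an unobserved subject as not closed is itself commonly regarded as imputation, so an unqualified ban points the other way. The protocol settles neither reading.

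Second, denominators are often left to the SAP, which section 10.1 promises and which was not available here. Silence alone would not be a finding. Here, though, the protocol states a rule, and an SAP that counts such subjects as not closed would have to interpret or depart from it.

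Third, a reader might infer that the arm losing more subjects looks better. With 2:1 allocation that is wrong by count: two ADRC losses and one control loss cancel, and one in each arm favours usual care.

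Fourth, exposure is limited. Visits before exit still count. Section 9.8 gives about 1 to 1.5 hospital days per 1% TBSA, so 20 × 1 = 20 to 50 × 1.5 = 75 days; many subjects would still be inpatients at weeks 2 to 4. The issue falls mainly on weeks 8 and 12.

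Fifth, avoiding model-based imputation with about five controls is defensible. The sample-size reason in section 10.6 is therefore not simply wrong. It does not, however, address how deaths and exits with an open wound are classified.

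**Conclusion.** The point holds as a gap between sections 10.5 and 10.6. On the plain reading, the closure percentages reported as ITT become observed-case percentages at visits after a death or withdrawal with an open wound.

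At 10 versus 5 subjects and an assumed 60% true closure in both arms, one or two such losses in one arm move the difference by 6.7 to 40 points. Across assumed closure of 40% to 80%, the smallest such shift is 4.4 points. Losing equal shares from arms with equal closure moves it by 0. These sizes rest on assumed rates and on counting by subject. If closure is counted by wound, as section 8.3 also suggests, losing one subject can remove up to three wounds.

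A reader might go further and conclude that the trial's main result is biased or that false significance would follow. The documents do not support that. The primary endpoints are safety and feasibility, closure is key secondary, section 10.2 says the sample is not powered for hypothesis tests, and no illustrative p-value is below 0.05. The change is worth making because the estimates are meant to inform a larger study.

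**What to change.** Amend section 10.6, and carry the change into the SAP:

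- In ITT, the denominator for complete closure is all randomized subjects in the arm at every scheduled visit.
- Death, withdrawal or loss to follow-up without documented closure counts as not closed from that point on.
- An intermittent missed visit is not automatically counted as not closed when closure is documented at the visits before and after it.
- Best-case and worst-case closure percentages are shown beside the result. These also cover subjects lost after documented closure.
- No imputation remains the rule for quantitative endpoints.

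Reconcile sections 5.5 and 8.11 on the content of the early-termination visit, so that closure status is recorded at exit up to week 12. State in the same place whether closure is counted by subject or by wound.

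The cost is a few sentences and, if sites now follow section 8.11, one more item at early-termination visits up to week 12. Closure percentages become slightly less favourable, and a subject who heals after leaving is counted as not closed. The bounds show how much that matters.

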## 10.7 Protocol Deviations

Deviations from the protocol, including violations of inclusion/exclusion criteria, will be assessed as “minor” or “major” by the Sponsor. Deviations will be defined prior to un-blinding.

## 10.8 Data Monitoring Committee

The independent Data Monitoring Committee (DMC) will be comprised of burn specialists and a biostatistician who are not participants in the study. The DMC will be provided with all safety data as well as efficacy data for the primary endpoint in order to fully evaluate the benefit to risk profile of the study procedures. The DMC will be responsible for the review of the data and generation of recommendations on the conduct of the trial.

The DMC will be asked to review data and generate recommendations after 5, 10, and 15 subjects have at least 1 week of follow-up. Enrollment after the first 5 subjects enrolled in active treatment may continue only after the DMC has completed its safety review and recommends continuation.

# 11 ADVERSE EVENTS / SERIOUS ADVERSE EVENTS

## 11.1 Definitions

An **Adverse Event (AE)** is defined as any undesirable experience occurring to a Subject during the course of the study, whether or not it is related to the test material or the study procedure. Expected adverse events are those that are listed as known risks of the tissue harvest or ADRC application procedure including those described in this protocol or the informed consent.

A **Serious Adverse Event (SAE)** is defined as any untoward medical occurrence that:

- Results in death
- Is life-threatening
- Requires or prolongs Subject hospitalization
- Results in persistent or significant disability or incapacity
- Is an important medical event(s) that may not be immediately life-threatening or result in death or hospitalization but that may jeopardize the Subject or require intervention to prevent one of the above outcomes
- Is a congenital anomaly/birth defect.

Medical and scientific judgment should be exercised in deciding whether a case is serious and whether expedited reporting is appropriate.

Pain and ecchymosis/hemorrhage around the fat harvest site are expected and should not be recorded as an adverse event unless meeting one or more of the following criteria: (a) serious adverse event (SAE), (b) greater severity than expected according to Investigator clinical judgment, or (c) hemorrhage requiring evacuation.

An **Unanticipated Adverse Device Effect (UADE)** is defined as any serious adverse effect on the health and safety or any life-threatening problem or death caused by, or associated with the Celution® system

device, if that effect, problem, or death was not previously identified in nature, severity, or degree of incidence in the investigational plan or application or any other unanticipated serious problem with the Celution® system device that relates to the rights, safety or welfare of subjects.

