#### **4.6 Study Endpoints**

##### ***4.6.1 Primary Endpoints***

- Safety and Feasibility

Safety will be evaluated based on the incidence, type and seriousness of adverse events related to the IV administration of test substance as well as the low volume lipoharvest procedure. Adverse events will be assessed according to the NIH Common Terminology Criteria for Adverse Events (CTCAE) v4.0 for scale grading adverse events.

Microbiological testing (culture and sensitivity) will be performed on the ADRC treatment dose produced and administered on site.

Feasibility will be determined as the ability to obtain  $> 100$  mL adipose tissue, obtain  $\geq 20 \times 10^6$  ADRCs, and deliver the prepared cell dose.

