### **9.3 Risks**

The primary risks associated with adipose tissue harvest are bleeding and infection associated with the removal of the adipose tissue (fat harvesting procedure) along with the potential risk of infection associated with intravenous delivery of ADRCs.

Tissue harvest by syringe-based manual aspiration has been used as a source for ADRCs in the 344 subjects in 7 clinical trials with the Celution system. Adverse events were those commonly associated with liposuction such as discomfort and ecchymosis. The only related serious adverse event reported was a single event of rectus sheath hematoma which was associated with the use of a glycoprotein IIb/IIIa inhibitor. The patient had unremarkable recovery. Fat harvest has been demonstrated to be feasible and is associated with an acceptable safety profile. The volume of adipose tissue removed in these studies generally varied between 150 mL and 450 mL. In the proposed feasibility and safety trial in burn patients a target volume between 100 to 150 mL of adipose tissue is to be removed and processed for ADRCs.

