## **9.10 Assessment of Uncertainty**

The key source of the uncertainty in the available evidence is the safety of the procedure in burn wound subjects and the level of potential effect on wound healing and the improvement in the clinical course of the subject. The safety profile of liposuction in subjects with burn wounds has not been established. Liposuction, in order to obtain ADRCs via the Celution system, has been used in seriously ill subjects in several studies that evaluated the effects of ADRCs on congestive heart failure and in subjects with an acute myocardial infarction (MI) within a 72 hour window post MI. No adverse events occurred secondary to liposuction other than the one subject with a rectus sheath hematoma whose had received a glycoprotein IIb/IIIa inhibitor. The procedure of low volume liposuction appears to be tolerated in subjects with significant myocardial decomposition. The safety of the subjects in this trial will be evaluated within a staggered enrollment with safety evaluations as well as by a Data Monitoring Committee (DMC).

The extent of benefit to subjects is unknown as no other clinical trial using intravenously administered ADRCs in the treatment of burn wounds has been done. Preclinical data generated in animal models of burn wounds suggests that wound healing should be accelerated.

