## 11.2 Procedures for AE Reporting

Adverse events will be assessed according to the NIH Common Terminology Criteria for Adverse Events (CTCAE) v4.0 for scale grading adverse events.

All AEs (including SAEs and UADEs) will be recorded by the investigator or designee on the appropriate electronic case report form (eCRF). Events that occur prior to the tissue harvest, including those that are considered serious, are to be recorded in the medical history. Events, including SAEs, which occur after tissue harvest procedure day, are to be recorded on the AE eCRF. The investigator will evaluate the relationship of the adverse event to both the test material and study procedure as unrelated, unlikely, possibly, probably, or definitely related and will record the findings, including all pertinent details of the event on the eCRF.

The investigator shall submit to the sponsor and to the reviewing IRB a report of any UADE occurring during an investigation as soon as possible, but in no event later than 10 working days after the investigator first learns of the effect.

In addition, the Investigator or designee will report any serious adverse events occurring during this study to the Cytori Medical Monitor as soon as possible, but no later than 24 hours after the Investigator first identifies the adverse event.

The Investigator will take appropriate measures to ensure the subject's well-being and document these measures on the appropriate eCRF.

All serious adverse events experienced will be monitored until the event has resolved, any abnormal laboratory values have returned to baseline or stabilized at a level acceptable to the Investigator and Medical Monitor, or until there is a satisfactory explanation for the changes observed.

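### Section 11.1 keeps non-serious harvest-site pain and bleeding of undefined 'expected' severity off the AE record, although the incidence of lipoharvest-related AEs is part of the primary safety endpoint

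*Protocol*

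**What the plan says.** Protocol section 4.6.1 defines the safety part of the primary endpoint: "Safety will be evaluated based on the incidence, type and seriousness of adverse events related to the IV administration of test substance". The same sentence names the lipoharvest as the second source of events. The Protocol Summary has the same definition. Section 10.3.1 analyses tissue-harvest events separately from those related to ADRCs and their delivery.

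Section 11.1 defines an adverse event broadly, as any undesirable experience during the study whether or not related. It then adds a special rule: "Pain and ecchymosis/hemorrhage around the fat harvest site are expected and should not be recorded as an adverse event unless" one of three criteria is met, listed as "a) serious adverse event (SAE), (b) greater severity than expected according to Investigator clinical judgment, or (c) hemorrhage requiring evacuation". No grade or description fixes what severity is expected.

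Section 11.2 states that "All AEs (including SAEs and UADEs) will be recorded by the investigator or designee" on the eCRF. Sections 4.6.1, 8.2, 10.3.1 and 11.2 call for CTCAE v4.0 grading.

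On background, section 9.3 names bleeding and infection as the primary harvest risks. Section 9.10 says: "The safety profile of liposuction in subjects with burn wounds has not been established".

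**The concern.** An endpoint defined partly by incidence needs its events to be recorded. Section 11.1 takes a class of harvest-site events out at data collection, and neither the endpoint text nor section 10.3.1 mentions this. A reader of the harvest-related AE table would take it as a count of all harvest-related events.

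The severity exception asks whether an event is worse than expected. Section 9.6 describes liposuction risks in healthy patients, and section 9.10 says safety in burn patients is not established, so the expectation has no stated basis in this population. With up to 10 centers and no reference grade, the same bruising could be recorded at one site and not at another.

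The omission would carry into the safety data that the DMC receives (section 10.8) and into the preliminary data meant for designing the larger study (section 10.2). A statistical analysis plan cannot repair it, because the events would not be in the database.

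**Working it through.** The protocol states no figure to reproduce: it gives no expected harvest AE rate and is not powered. The check is a comparison of passages, followed by an illustration.

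**1. What is lost and what is kept**

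| Harvest event | Reaches the safety record? | Source |
|---|---|---|
| Any SAE | Yes | 11.1, exception (a) |
| Pain or bleeding judged worse than expected | Yes, by investigator judgment | 11.1, exception (b) |
| Hemorrhage requiring evacuation | Yes | 11.1, exception (c) |
| Events that terminate the harvest (e.g. profuse bleeding, perforation) | Yes, on the SAE form | 8.7.1.3 |
| Infection, edema, deep vein thrombosis | Yes, not named in the exclusion | 9.6, 11.1 |
| Non-serious, non-evacuated pain or ecchymosis/hemorrhage of expected severity | **No** | 11.1 |

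The protocol describes no other collection of the last row. The pain scale in section 8.3 and Appendix A is for the wound, and the schedule has no harvest-site assessment.

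**2. Harvested subjects**

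Up to 15 subjects (section 4.3) at 2:1 (section 5.2) gives 15 × 2/3 = 10 harvested. Controls have no harvest.

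**3. How large the under-count could be (assumed inputs)**

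Let p be the true proportion of harvested subjects with harvest-site pain or ecchymosis/hemorrhage, and r the share of those whose event meets an exception. The protocol gives neither. Treating subjects as independent:

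- expected affected = 10p
- expected recorded = 10pr
- chance that none is recorded = (1 − pr)^10

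| p | r | Affected | Recorded | Chance of 0/10 recorded |
|---|---|---|---|---|
| 0.3 | 0.05 | 3 | 0.15 | 86% |
| 0.3 | 0.20 | 3 | 0.6 | 54% |
| 0.5 | 0.10 | 5 | 0.5 | 60% |
| 0.5 | 0.50 | 5 | 2.5 | 6% |
| 0.9 | 0.05 | 9 | 0.45 | 63% |
| 0.9 | 0.20 | 9 | 1.8 | 14% |

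For example, p = 0.5 and r = 0.10 give (1 − 0.05)^10 = 0.599. The result depends strongly on r: if half of the affected subjects met an exception, a table of zeros would be unlikely at p = 0.5.

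**4. How 0/10 would read**

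The exact two-sided 95% upper limit for 0/10 is 1 − 0.025^(1/10) = 0.308, about 31%. With p = 0.5, a recorded 0/10 would suggest a ceiling below the true 50%. The protocol plans descriptive summaries only, so this interval shows how a reader might interpret the table. It is not a planned analysis.

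**The case against.** Sponsors may prespecify expected sequelae of a procedure as non-events, and the rule is narrower than its opening clause suggests. Three exceptions restore recording, and two of them admit non-serious events. Section 8.7.1.3 sends major bleeding and perforation to the SAE form. Section 9.6.1 requires hemoglobin and hematocrit before and 1–2 hours after the procedure, and section 8.8 a blood count at the first dressing change. Clinically important bleeding is therefore not left to the severity exception alone. This stands, and it limits the point to non-serious events of expected severity.

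Four stronger readings are tempting, and the document does not support them:

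- **A contradiction with section 11.2 and the CTCAE requirement.** Section 11.1 can be read as a carve-out from what counts as an AE, and a non-AE need not be recorded or graded. The clearer tension is with the broad AE definition in section 11.1 itself and with an endpoint that does not mention the carve-out.
- **Half of the primary safety endpoint is affected.** Section 4.6.1 names two sources of events without weighting them, and feasibility is also primary.
- **Bias from unblinded judgment.** Controls have no harvest, so there is no between-arm comparison of harvest-site events to distort. The problem is consistency between sites.
- **Lost comparability with earlier Celution trials.** Section 9.3 says of them: "Adverse events were those commonly associated with liposuction such as discomfort and ecchymosis". But section 9.10 reports no adverse events from liposuction in the cardiac studies apart from one hematoma, and the earlier recording rules are not given.

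The objection does not remove the core. Blood counts do not count or grade pain and bruising, and none of these safeguards restores the incidence of the excluded events.

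**Conclusion.** The point holds in limited form. As written, section 11.1 makes the harvest-related part of the primary safety endpoint incomplete in incidence and, for mild events, in type. Seriousness is preserved. The boundary of what is recorded rests on an undefined expectation in a population that the protocol itself calls uncharacterised.

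The size of the under-count cannot be derived from the document. Under the assumed ranges p = 0.3 to 0.9 and r = 0.05 to 0.20, the chance that none of 10 harvested subjects has a recorded event runs from 14% to 86%. These figures assume full enrollment, an exact 2:1 split and independence between subjects.

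A reader might infer that harvest-site bleeding never reaches the safety table, or that the reported rate will be close to zero. Neither follows, because the exceptions and the harvest-stopping rules admit the more important events. What does follow is that a low recorded rate could not be told apart from an effect of the recording rule. The correction is cheap and has to be in place before data are collected.

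**What to change.** Replace the exclusion in section 11.1 with an instruction to record harvest-site pain and ecchymosis/hemorrhage on the AE eCRF for every harvested subject, each with a CTCAE v4.0 grade and an 'expected' flag. In section 10.3.1, present the harvest-related AE table with and without the flagged events. Expectedness may still govern expedited reporting, but should no longer decide whether an event is recorded.

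If the sponsor prefers to keep an exclusion, the less complete alternative is to state it in the endpoint definition (Protocol Summary and section 4.6.1) and to give the severity exception a defined grade. That makes the endpoint honest and the threshold uniform, but the excluded events would still not be counted.

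The cost of the main change is a revised instruction in section 11.1, a line in section 10.3.1 and a few more eCRF entries for about 10 subjects. The harvest AE rate will look less favourable, and the 'expected' flag lets readers see why. No clinical management changes.
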